11. Subject Population: Describe the characteristics of the participant population including the inclusion and exclusion criteria and the number of participants you plan to recruit:

A total of 40 clients admitted to the Opioid Diversion Program (ODP) will be enrolled for the T-CAP study and all will receive the T-CAP intervention. Since the sample will be drawn from the existing ODP, sociodemographic characteristics are expected to be similar to census demographics for the corresponding communities, with approximately 59% male, 88% white, and average age of 32. In addition, we expect approximately 40% will need mental health services as part of their treatment and 60% will need services for medical problems. The ODP screens out individuals who have a criminal record of violent offenses. While all current ODP clients have a recent history (within the past 12 months) of opioid use or other substance use, we will confirm this during the RA's administration of the TCU Drug Screen 5 and TCU Drug Screen 5—Opioid Supplement. If this process reveals that the individual does not have a recent history of opioid or substance use, they will be offered the opportunity to remain in the study but excluded from the primary analyses. Furthermore, individuals who are not willing to consent to granting research staff permission to access their police and treatment services records, and individuals who do not understand the informed consent (see appendix for the Informed Consent Comprehension Questions), will be excluded from the study. Individuals must demonstrate the ability to speak and understand English and be at least 18 years old to participate in this study. At the Informed Consent meeting, the RA will determine that these criteria are met.

[figure not shown]
12. Recruitment Procedure: Describe your recruitment strategies including how the potential participants will be approached and precautions that will be taken to minimize the possibility of undue influence or coercion. Include copies of the recruitment letters, leaflets, etc. in your submission.

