The standing video call arrangements will be entered into the tracking spreadsheet by the Coach and uploaded to TCU Box. The Coach will then alert the RA that the spreadsheet is ready for download. The RA will download and proceed to set up the 6 remaining telehealth sessions in the app scheduling feature. The RA will send a confirmation text or email to the participant with the schedule. The day prior to each of the 6 telehealth calls, the app will generate an automated reminder message about the upcoming telehealth call. We anticipate that there will be changes to the video call schedules, and participants will be advised to contact the RA for any schedule changes on video calls.

T-CAP Intervention. Coaching will be provided to the total study sample (N=40) by two licensed substance use treatment counselors, currently available through the Lake County Health Department. The Coach position requires professional training as a substance abuse counselor or equivalent (e.g., counselor with mental health credentials). Each Coach will be responsible for 20 participants during the 11-month implementation period. The study calls for two half-time Coaches, one to cover responsibilities in the event that one Coach is not available (e.g., due to vacation). In the event that one or both Coaches are unable to continue the study, replacements will be engaged for the project [the IBR has a strong collaborative relationship with several behavioral service providers in Lake and Cook Counties in Illinois.] Each participant will be assigned to only one of the Coaches for the duration of the intervention.

The 12-week telehealth intervention features 7 video calls on a smart phone, that will connect the participant with a Coach who will deliver the 3 components of the intervention: brief Motivational Interviewing (MI) sessions (see Appendix for MI scripts), recovery support, and assertive referrals to services that are intended to augment ODP substance use treatment or during post-treatment when there is an additional treatment need during recovery, as identified by the participant.

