resources to complete the assertive referrals, the RA will maintain an Excel spreadsheet with area providers, available services, payment options, and contact information. Before the end of the telehealth session, the Coach will also confirm the next scheduled telehealth session with the participant. Overall, the telehealth sessions with MI and coaching support are expected to last up to 30 minutes. In addition to the Coach-initiated telehealth sessions, participants will be encouraged by the Coach to request additional telehealth sessions as needed. Participants will send a text message to the RA requesting a video call. The RA will reply via text message with scheduling options, based on availability of the Coach. We anticipate that special requests for video calls will be a response to a pressing issue that is weighing on the participant, so these calls will occur within the same day as the request whenever possible. The T-CAP research procedures for RA and Coach will be monitored with a monthly Procedural Fidelity Checklist (included in the Appendix).

Telehealth app data collection. There are two types of data from the T-CAP app: (1) function data (e.g., frequency of messaging, date/time of video calls and duration of calls), and (2) two telehealth satisfaction questions completed by participants at the end of each telehealth session (see appendix). Both data types will be available for download (from the cloud) to TCU Box. The data will be identified by the phone number. The phone number will be replaced with the Research ID by the Project Coordinator, so that no identifying information will be included in the analytic dataset.

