Completed Provider Data Request Forms will be uploaded by the provider to TCU Box and available for download by authorized project staff. Data from the forms will be entered into a provider data tracking Microsoft Excel file at the IBR and maintained on a secure server at the IBR office.

14. Data Analyses: Describe how you will analyze your data to answer the study question

Aim 1: Demonstrate intervention feasibility by measuring study participant receptivity and utilization of the telehealth approach. Feasibility will be primarily assessed by descriptive analyses of participation, satisfaction, and telehealth usability data. We will examine distributions on these measures as well as characteristics of participants with high and low participation sample size, we will be more interested in trends than in statistical significance. Receptivity and utilization will be assessed by self-report measures as well as participation data from the T-CAP app. Self-report measures will include the Telehealth Usability Questionnaire (TUQ), Telehealth Session surveys, and semi-structured closeout interviews. The TUQ gauges constructs that are consistent with those in the telehealth literature and include: Usefulness, Ease of Use Interaction Quality, Satisfaction and Future Use, Interface Quality; and Reliability. TUQ scores of 4.0 (agree) and above on each domain indicate high receptivity. Scores below 4.0 will be interpreted as an indication that the participant encountered some challenge in that area of using the telehealth system. Data from the TCAP app will provide evidence of utilization (i.e., process data on session completion, duration, and number of unscheduled contacts). Two satisfaction questions are asked after each video conferencing session. We will primarily examine counts and distributions of these data but will also examine characteristics of participants with high and low levels of participation. All individuals will be invited to participate in an interview with a member of the research team. Our goal is to obtain feedback at the study closeout (Time 3) from a minimum of 6-8 participants. Drawing on our extensive qualitative experience, a semi-structured interview with questions from the TUQ, paired with relevant probes, will guide the interview to help us gain a better understanding about how the telehealth experience impacted participants.

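### Aim 1 relates participant characteristics to telehealth uptake only through an undefined high/low grouping, although uptake is recorded as counts and durations; a cheap improvement to an exploratory description

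*Combined protocol and SAP*

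**What the plan says.** Section 11 sets the sample: "A total of 40 clients admitted to the Opioid Diversion Program (ODP) will be enrolled for the T-CAP study", all receiving the intervention. People found to have no recent opioid or substance use may stay in, but "they will be offered the opportunity to remain in the study but excluded from the primary analyses".

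Participation is measured finely. Under T-CAP Intervention, "The 12-week telehealth intervention features 7 video calls on a smart phone", so planned calls completed run from 0 to 7. Under Telehealth app data collection, the app supplies "function data (e.g., frequency of messaging, date/time of video calls and duration of calls". Section 14, Aim 1, takes as its evidence of utilization "process data on session completion, duration, and number of unscheduled contacts".

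The main handling of these data is descriptive: "We will primarily examine counts and distributions of these data". The plan adds that it "will also examine characteristics of participants with high and low levels of participation", a look mentioned twice in the Aim 1 paragraph. It gives no definition of high or low, no measure to be split, no rule for a middle group and no test. The paragraph says that trends interest the investigators more than significance.

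Aim 2 compares demographics and baseline opioid use between people who complete all 7 calls and people who do not. That is again a two-group split, though with a stated cut. Correlations are named only under secondary outcomes, for differences between those same two groups.

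**The concern.** In Aim 1, participation is the outcome, and the added question is who takes telehealth up. Counts and distributions describe uptake itself. The high/low grouping is the only stated Aim 1 step that links uptake to who the participants are.

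A grouping of this kind has two weaknesses. First, it treats people just either side of the cut as opposites and people far apart on the same side as identical. Each association is then estimated less precisely than the recorded data allow. Second, with no cut fixed, the analyst can place it after seeing the data, and the apparent pattern may depend on where it falls. An interest in trends rather than tests removes neither weakness, because the trend itself becomes noisier and open to selection.

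At stake are the early signals about who engages. The documents expect the findings to inform a later grant application, so these signals are worth estimating well.

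**Working it through.** **Inputs.** N = 40 (section 11) and planned calls 0 to 7 (T-CAP Intervention). The plan gives no power, alpha, cut, expected correlation or efficiency figure, so there is nothing of its own to reproduce. Everything below assumes a shape for participation, a cut and, for power, a correlation r and a two-sided 0.05 test. Power serves only as an index of precision, since no test is planned.

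**1. One cut of a normal measure.** The share of information kept, relative to a Pearson analysis of the full measure, is φ(z_p)² / [p(1−p)], where p is the proportion in one group. At the median this is 0.3989² / 0.25 = 2/π = 0.637, a 36% loss; 40 × 0.637 = 25.5 people's worth.

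| Split | Loss | Equivalent n of 40 |
|---|---|---|
| 50/50 | 36% | 25.5 |
| 33/67 | 41% | 23.8 |
| 25/75 | 46% | 21.5 |
| 10/90 | 66% | 13.7 |

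Comparing the top with the bottom third, and dropping the middle, loses about 21%.

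**2. Against Spearman, the analysis proposed below.** For normal data Spearman keeps 9/π² = 0.912 of Pearson's information. The split therefore keeps 0.637 / 0.912 = 0.698 of Spearman's: a 30% loss, or 40 × 0.698 = 27.9 people.

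**3. Calls scored 0 to 7.** Information kept is the squared correlation between the count X and the indicator X ≥ k. Example, uniform on 0 to 7 and k = 4: variance 5.25, covariance (5.5 − 3.5) × 0.5 = 1, so 1² / (5.25 × 0.25) = 0.76, a 24% loss. The best cut under each assumed shape loses:

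- 18% (U-shaped, beta-binomial 0.5, 0.5)
- 20% (piled near 7, beta-binomial 1, 0.3)
- 24% (uniform)
- 27% (beta-binomial 2, 1)
- 32% (binomial 0.7)

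Cutting at all 7 calls versus fewer, the only participation cut the documents define, loses 45% to 73% under the same shapes.

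**4. Power at N = 40.** 6,000 simulated datasets per setting, one roughly normal characteristic. Spearman on the full scale is compared with a t-test of the characteristic between groups cut nearest 50%. The calls columns span four assumed beta-binomial shapes: (1.5, 1), (2, 1), (1, 1) and (0.6, 0.4).

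| r | Minutes: Spearman | Minutes: split | Calls: Spearman | Calls: split |
|---|---|---|---|---|
| 0.3 | 0.435 | 0.324 | 0.414–0.426 | 0.317–0.328 |
| 0.4 | 0.685 | 0.530 | 0.655–0.677 | 0.528–0.538 |
| 0.5 | 0.885 | 0.740 | 0.861–0.879 | 0.739–0.750 |

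With no association, both methods reject in 4.6% to 5.2% of datasets. The first row agrees with step 2. Powers 0.435 and 0.324 correspond to standardized effects of 1.96 − 0.164 = 1.796 and 1.96 − 0.457 = 1.503, and (1.503 / 1.796)² = 0.70.

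**5. Choosing the cut afterwards.** With no true association, taking the most striking of the possible call cuts (groups of at least 4) gave p < 0.05 in roughly 18% to 20% of simulated datasets instead of 5%. That is for a single characteristic.

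**The case against.** The strongest reply is that the plan states no split to criticize. Examining the characteristics of high and low users may mean no more than describing who used the app more and who used it less. Feasibility is assessed mainly by description, no test or alpha is attached, and power is computed here for a test nobody plans. This largely stands: it makes the matter exploratory and the size conditional. It does not supply an analysis of characteristics against uptake as recorded, and it leaves the cut open.

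Aim 2 also relates characteristics to participation, with a cut stated in advance. True, but it is again a two-group split, and at a cut that may lose more information than a median one.

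A reader might infer three stronger things.

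- That the plan wastes a third of its information as a matter of fact. It fixes no cut, so no single figure applies.
- That the feasibility conclusion is weakened. It rests mainly on the counts and distributions of participation and on the satisfaction and usability data, which the grouping does not touch.
- That these contrasts will set the tailoring of T-CAP to subgroups. The objectives ahead of section 10 give that closer look to the future multi-site trial. The examples named there, sex and race/ethnicity, are categorical, and the simulation does not cover them.

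Finally, the first mention of the high/low look is broken in the extracted text, so claims about what is unstated need some caution. The second mention is intact and also gives no definition.

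**Conclusion.** The point holds as a cheap improvement to a secondary, exploratory description. Within Aim 1, the only stated link between characteristics and uptake is an undefined high/low grouping of measures recorded as counts and durations. For a near-median split of a roughly normal measure, the loss is about 30% relative to Spearman (about 28 of 40 people's information kept) and 36% relative to Pearson (about 25 of 40). Relative to the full-scale linear analysis, other cuts and shapes lose from about 20% to over 60%. The correlations and participation shapes are assumptions. Any exclusions under section 11 would lower the analysed number below 40. The open cut needs no such assumption: nothing in the text prevents choosing it after the data are seen.

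**What to change.** In section 14, Aim 1, state that baseline characteristics will be related to participation on its recorded scale, mainly planned calls completed (0 to 7) and total call minutes.

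- **Continuous or ordinal characteristics:** Spearman correlations with 95% confidence intervals.
- **Categorical characteristics:** mean or median differences in participation with 95% confidence intervals.
- **Population:** the analysis population described in section 11, with participants who took no calls scored 0.
- **Unscheduled contacts:** reported separately. The Study Procedures expect requests for extra calls to be prompted by urgent problems, so they partly measure need as well as uptake.
- **Status:** all of these estimates labelled exploratory.
- **High/low table:** kept if wanted, as a display only, with the measure and cut fixed before the data are viewed.

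The cost is a few sentences and no new data, since the app already records these measures. The downside is a summary that is less immediate to read than two columns, and several exploratory estimates from a small sample.

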Aim 2: Evaluate the proposed T-CAP measures to assess their performance in gauging the impact of telehealth on initiation of in-person Substance Use (SU) treatment, short-term retention in referred SU treatment, and access to other appropriate treatment services (e.g., MAT). Our multidimensional approach includes data from self-report attendance and treatment engagement, self-report drug use, Coaches' advocate records on number of completed assertive referrals, and agency records from police and BH providers (including intake and during-program UA test results). In order to examine groups differences for intervention completers (C) vs non-completers (NC) (i.e., individuals who do not complete the 7 coaching video calls), group differences using t-tests and chi-square tests and we will estimate effect sizes needed for determining a sample size for a future R01 proposal. To assess potential assignment bias, we will test to see if there are baseline differences in demographics: participant race, gender, age and other demographic characteristics, as well as baseline measures of opioid use frequency and amount will be examined using chi-square and t-tests. Effect sizes will be computed for group differences on multiple outcomes (treatment initiation, retention, referrals to expanded SU service options, missed appointments). Service attendance records will be corroborated monthly with service provider records. Examinations of referrals to MAT and alternative pain management care between the C and NC groups, utilizing agency records data and the Coach tracking, will be conducted using a z-score to test differences in proportions of referral types. This will be calculated for all assertive referrals (resulting in scheduled appointments) collectively for a participant, as well as for different types of services.

Analyses of Secondary outcomes. We will examine differences between C and NC groups on several secondary outcomes. Analyses will typically involve t-tests, chi-square tests, and correlations. For example, we will use t-tests to assess differences between groups on the 3-month follow-up measures

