of treatment motivation and psychosocial function from the TCU Client Evaluation of Self and Treatment (TCU CEST), a widely used form listed on the IBR web page. Validation of recent (last few days) self-reported opioid use will be compared with drug testing outcomes at each assessment time point using McNemar's test for change of state, as well as computing sensitivity and specificity statistics and the kappa statistic as a measure of agreement. We will compare self-report, as well as urinalysis (UA) results from agency drug screens between the two groups.

15. Potential Risks and Precautions to Reduce Risk: Indicate any physical, psychological, social, or privacy risk which the subject may incur. Risk(s) must be specified. Also describe what measures have been or will be taken to prevent and minimize each of the risks identified. If any deception is to be used, describe it in detail and the plans for debriefing.

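### Aim 2 asks how well the initiation, retention and access measures perform, but section 14 plans only completer versus non-completer contrasts for them, with no source agreement, completeness or named analysed source

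*Combined protocol and SAP*

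**What the plan says.** The specific aims and section 14 of the combined protocol and SAP both word Aim 2 as a question about measures: "Evaluate the proposed T-CAP measures to assess their performance in gauging the impact of telehealth on initiation" of in-person treatment, short-term retention, and access to other services.

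The data are drawn from several places: "Our multidimensional approach includes data from self-report attendance and treatment engagement, self-report drug use, Coaches' advocate records on number of completed assertive referrals", together with police and provider records. Under Agency Records in the Study Procedures, a monthly provider form collects, among other items, the date treatment started, sessions scheduled and missed, drug test results and the discharge date.

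The analyses written for the three named outcomes are:

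- Completers versus non-completers of the seven calls: "group differences using t-tests and chi-square tests and we will estimate effect sizes needed for determining a sample size for a future R01 proposal".
- "Effect sizes will be computed for group differences on multiple outcomes (treatment initiation, retention, referrals to expanded SU service options, missed appointments").
- For referrals to medication-assisted treatment and alternative pain care, a comparison that "will be conducted using a z-score to test differences in proportions of referral types".
- For attendance: "Service attendance records will be corroborated monthly with service provider records".

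Under Analyses of Secondary outcomes, one measure does get a performance analysis: "Validation of recent (last few days) self-reported opioid use will be compared with drug testing outcomes at each assessment time point using McNemar's test", plus "computing sensitivity and specificity statistics and the kappa statistic as a measure of agreement".

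**The concern.** A difference between two groups, or its absence, does not say whether a measure is complete or accurate. To learn how a measure of initiation, retention or access performs, one needs to know how often it yields a usable value and how closely it matches another source on the same person. The plan collects sources that overlap at least in part, but attaches neither statistic to these three outcomes and sets no criterion for adequate performance. Attendance discrepancies are looked for each month without being counted, and nothing says which source enters the analysis when two conflict.

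At stake is what the study passes on to the R01. Without these results the sponsor would not know how much of each source is missing or how far the sources disagree. The effect sizes meant for the R01 sample size would also carry an unknown amount of measurement error.

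**Working it through.** **1. No figure to reproduce.** The plan gives no agreement target, error rate, alpha, power or precision goal behind the 40 participants. The check is therefore one of aim against analysis, with illustrations that rest on stated assumptions.

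**2. Aim against analysis.**

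| Measure | Planned group contrast | Planned performance analysis |
|---|---|---|
| Treatment initiation | Effect size, t-test or chi-square | None |
| Retention, missed appointments | Effect size, t-test or chi-square | None; attendance corroborated, discrepancies not quantified |
| Access and referrals | Effect size, z test of proportions | None |
| Self-reported opioid use | Self-report and urinalysis compared between groups | McNemar, sensitivity, specificity, kappa |

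Only the last row has an entry that answers a question about performance, and it is not one of the three outcomes named in the aim.

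**3. Why a contrast does not fill the gap.** Suppose a yes/no source misclassifies a proportion *e* of participants in each direction, equally in both groups. A true proportion *p* is then seen as *e* + *p*(1 − 2*e*), so the observed gap is the true gap × (1 − 2*e*). Assume true retention of 70% and 40%, a gap of 30 points:

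- *e* = 10%: 66% versus 42%; 30 × 0.8 = 24 points
- *e* = 20%: 62% versus 44%; 30 × 0.6 = 18 points
- *e* = 30%: 58% versus 46%; 30 × 0.4 = 12 points

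Nothing planned for these outcomes would separate an observed 12 points of this kind from a true 12 points. The shrinkage depends on equal error. If completers were recorded without error and 30% of retained non-completers were missed, the source would show 70% versus 40 × 0.7 = 28%, a gap of 42 points. Error can therefore move the gap either way.

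**4. What the contrast can deliver.** With two-sided 5% and 80% power (both assumed), the smallest detectable standardized difference is (1.96 + 0.84) × √(1/n₁ + 1/n₂). That is 0.89 for a 20/20 split and 1.02 for 30/10. The 95% half-width, 1.96 × √(1/n₁ + 1/n₂), is 0.62 and 0.72. These figures describe contrasts only.

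**5. What an agreement analysis would deliver.** Exact (Clopper-Pearson) 95% intervals for percent agreement with 40 pairs: 32/40 (80%) gives 64% to 91%; 36/40 (90%) gives 76% to 97%.

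For kappa, using the large-sample Fleiss-Cohen-Everitt standard error with equal marginals, take kappa 0.6, prevalence 50% and 40 pairs. The cells are 0.40, 0.10, 0.10 and 0.40, and chance agreement is 0.5. The variance is (0.288 + 0.032 − 0.160) / (40 × 0.25) = 0.016, the standard error 0.126 and the half-width 1.96 × 0.126 = 0.25.

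| Pairs | Kappa | Half-width at prevalence 50% | 70% | 85% |
|---|---|---|---|---|
| 40 | 0.6 | 0.25 | 0.27 | 0.35 |
| 40 | 0.8 | 0.19 | 0.20 | 0.26 |
| 24 (40% missing, assumed) | 0.6 | 0.32 | 0.35 | 0.45 |

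**6. Which pairs exist.** The provider form covers initiation and attendance, and section 14 lists self-reported attendance. The listed form items include no referral or medication-assisted treatment field. Forms are requested for participants receiving services at an agency, so someone who never starts treatment may have none. Among those with a form, provider-side initiation may be almost always yes; kappa would then be uninformative, and the start date and the count without a form matter more.

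**The case against.** The aim speaks of performance in gauging impact, and whether measures separate groups, and by how much, is a form of performance. Effect sizes for the R01 are a stated product of the plan. This stands in part: the contrasts give weak known-groups information and should be kept. But all participants receive the intervention, the groups form after enrolment by completion of the calls, and no true difference is known in advance against which to judge a measure. That grouping also limits what can be said about impact, which is a separate matter.

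A reader might infer that Aim 2 cannot be answered at all. The documents do not support that. Self-reported drug use belongs to the Aim 2 data and is validated against drug tests, and provider data on initiation and attendance are already collected.

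A reader might also infer that monthly corroboration erases disagreement between sources. No text describes overwriting. Survey downloads, Coach caseload files and provider data are kept in separate files (Study Procedures and section 16). The corroboration sentence concerns attendance alone.

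Finally, agreement between two fallible sources shows that they differ, not which is wrong, and 40 pairs or fewer give wide intervals. Both points stand. They limit how firmly a source could be chosen for the R01 but are no reason to leave completeness and disagreement unreported.

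**Conclusion.** The concern holds in a bounded form. For initiation, short-term retention and access, the planned analyses do not show how well the measures perform, because they are all completer versus non-completer contrasts. For attendance, discrepancies are sought but not quantified, and the analysed source is not stated. This should be changed, but it does not threaten the feasibility aim.

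The size cannot be derived from the documents. The fall from 30 points to 24, 18 or 12 is an illustration under assumed rates and equal error in both groups. It should not be read as showing that the effect sizes will be too small: with unequal error they could be too large. Nor should one conclude that every part of the gap closes without new data. That is secure on the provider side for initiation and attendance, but not for access, where no provider item is listed to pair with Coach tracking. The survey instruments are in an appendix not available here, so which self-report items can be paired remains open.

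**What to change.** In section 14, keep each source's value as first recorded and add to the Aim 2 results:

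1. **Completeness.** For initiation, attendance/retention and access, the percentage of the 40 participants with a usable value in each source. Participants with no provider form stay in the denominator and are shown as a separate count.
2. **Agreement**, where two sources cover the same person and period. Compare the provider form with self-report for initiation and attendance, with monthly provider windows aligned to the week 6 and week 12 surveys. Give percent agreement and kappa for yes/no items, and intraclass correlation or limits of agreement for counts and dates, all with 95% intervals.
3. **Access.** Report completeness, and compare Coach tracking only with any agency or self-report item that exists.
4. **Analysed source.** State which source enters the group contrasts, and repeat the contrasts with the other as a sensitivity analysis.

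Keep the planned effect sizes beside these results. The cost is a change to section 14, a column per source in the tracking files and a small amount of analysis. The limitation is precision: a 95% half-width of about 0.25 to 0.35 for an assumed kappa of 0.6 with 40 pairs, and wider with fewer, so the results should be presented as descriptive.
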